The incidence of the olecranon fracture (OF) in adults is around 12 per 100,000 inhabitants per year.¹ The anatomical shape of the proximal ulna is largely responsible for the stabilization of the humeroulnar joint and reconstruction is therefore obligatory, but often challenging. Surgical treatment of the olecranon fracture is performed using tension band wiring (TBW) or locking plate fixation (LPF) osteosynthesis. It is not yet clear, which procedure is superior for a specific patient. In future, an individualized and objectified assessment of expected general and fracture-specific complications should enable the treatment to be individually adapted to the patient's risk profile. This shall prevent complications, unnecessary treatments, and treatment costs. In the project presented here, the reality of care for surgically treated patients with olecranon fractures will be analyzed using routine data collected by the BARMER health insurance fund.

The aim of the study is to analyze differences in the outcome of patients with an olecranon fracture treated with TBW compared to LPF and to identify independent risk factors for unfavorable course.

2. Population

The German reimbursement system governs the remuneration of health care services subject to encoded diagnoses (International Statistical Classification of Diseases, German Modification; ICD-10 GM) and procedures (German procedure classification – *Operationen- und Prozedurenschlüssel*; OPS) by means of the 'German Diagnosis Related Groups' taxonomy (GDRG). This obligatory documentation and accounting system is specified and further regulated in detail by mandatory coding instructions.

The database consists of retrospective health claims data of the German BARMER health insurance company. This includes anonymized data from following sectors:

- Inpatient data (§301 SGB V): In addition to information on costs, duration of hospitalization and information about treating hospital, standardized information on diagnoses (coded according to ICD-10 GM) and procedures (coded according to OPS) are available.
- Outpatient data (§295 SGB V): In addition to information on costs, diagnoses (ICD-10 GM) and procedures (OPS).
- Pharmaceutical therapies (§300 SGB V): Information on medication (coded via ATC classification), as well as costs and DDD (Defined Daily Dose).

All adult patients with an age of 18 years and older with an inpatient treated OF (ICD S52.01) treated with LPF or TBW between 01/2011 and 09/2023 will be included to the evaluations. Patients were grouped by age (i.e. 18-44 years, 45 – 69 years, ≥ 70 years). Younger patients (<70 years) and older patients (≥ 70 years) will be analyzed in separate studies.

2.1. Treatment Groups

The patient population will be divided into four treatment groups based on the first treatment received.

Group 1: *Locking Plate fixation for simple fractured OFs (sLPF)*

Patients allocated to this treatment group received a locking plate fixation after the first coded diagnosis of simple fractured OF.

Group 2: *Locking Plate fixation for multi-fragmented OFs (LPF)*
 Patients allocated to this treatment group received a locking plate fixation after the first coded diagnosis of multi-fragmented OF.

Group 3: *Tension band wiring for simple fractured OFs (sTBW)*
 Patients allocated to this treatment group received a tension band wiring fixation after the first coded diagnosis of simple fractured OF.

Group 4: *Tension band wiring for multi-fragmented OFs (TBW)*
 Patients allocated to this treatment group received a tension band wiring fixation after the first coded diagnosis of multi-fragmented OF.

If TBW and LPF were coded at the same day and side, patients will be allocated to the LPF groups.

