2.2. Inclusion and Exclusion Criteria

Within an index period from 01/2011 to 09/2023 all patients will be included, who met all inclusion criteria and no exclusion criterion (see table 1).

Inclusion Criteria
Inpatient coded diagnosis of olecranon fracture (ICD S52.01)
Exclusion Criteria
Incomplete basic information
Incomplete insurance status within two years before index
Previous treatment of olecranon fracture
Unclear treatment of olecranon fracture (other as variable and code from table 2)
Age < 18 years
Coded polytrauma
Bone tumors/ bone metastasis
Both sides injured or missing information of surgery side

Table 1: Inclusion and exclusion criteria.

The first hospitalization within the index period with coded diagnosis for OF (S52.01 main and secondary diagnosis) and at least one coded surgical treatment using TBW (OPS 5-793.27, 5-794.17) or LPF (OPS 5-793.k7, 5-794.k7) will be defined as the index case. In addition, all overlapping cases without time delay (admission date new case = discharge cases with surgery) will be defined as one case-series and will be included in the index case.

3. Endpoints and Variables

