Secondary surgery, open (LPF and TBW)	OPS	5-780.07, 5-780.17, 5-780.27, 5-780.37, 5-780.67, 5-780.x7, 5-782.17, 5-782.27, 5-782.37, 5-782.47, 5-782.57, 5-782.a7, 5-784.07, 5-784.17, 5-784.27, 5-784.37, 5-784.47, 5-784.57, 5-784.67, 5-784.77, 5-784.87, 5-784.a7, 5-784.b7, 5-785.07, 5-785.17, 5-785.27, 5-785.37, 5-785.47, 5-785.57, 5-785.67, 5-785.77, 5-789.b7, 5-789.c7, 5-794.07, 5-794.27, 5-794.57, 5-794.67, 5-794.77, 5-794.87, 5-800.14, 5-800.15, 5-800.34, 5-800.35, 5-800.44, 5-800.45, 5-800.54, 5-800.55, 5-800.74, 5-800.75, 5-800.84, 5-800.85, 5-800.94, 5-800.95, 5-800.x4, 5-800.x5, 5-801.04, 5-801.05, 5-801.34, 5-801.35, 5-801.44, 5-801.45, 5-801.b4, 5-801.b5, 5-801.c4, 5-801.c5, 5-801.g4, 5-801.g5, 5-801.h4, 5-801.h5, 5-801.k4, 5-801.k5, 5-801.m4, 5-801.m5, 5-801.n4, 5-801.n5, 5-801.p4, 5-801.p5, 5-850.02, 5-850.12, 5-850.22, 5-850.32, 5-850.42, 5-850.52, 5-850.62, 5-850.72, 5-850.82, 5-850.92, 5-850.a2, 5-850.b2, 5-850.c2, 5-850.d2, 5-850.e2, 5-850.f2, 5-850.g2, 5-850.h2, 5-850.j2, 5-851.12, 5-851.22, 5-851.32, 5-851.42, 5-851.52, 5-851.62, 5-851.72, 5-851.82, 5-851.92, 5-851.a2, 5-851.b2, 5-851.c2, 5-851.d2, 5-852.02, 5-852.12, 5-852.22, 5-852.32, 5-852.42, 5-852.52, 5-852.62, 5-852.72, 5-852.82, 5-852.92, 5-852.a2, 5-852.b2, 5-852.c2, 5-852.d2, 5-852.h2, 5-852.j2, 5-853.02, 5-853.12, 5-853.22, 5-853.32, 5-853.42, 5-853.52, 5-853.62, 5-853.72, 5-853.82, 5-853.92, 5-853.x2, 5-855.02, 5-855.12, 5-855.22, 5-855.32, 5-855.42, 5-855.52, 5-855.62, 5-855.72, 5-855.82, 5-855.92, 5-855.a2, 5-855.b2, 5-859.02, 5-859.12, 5-862.2, 5-862.3, 5-862.4, 5-892.07, 5-892.17, 5-892.27, 5-892.37, 5-892.47, 5-896.07, 5-896.17, 5-896.27
Secondary arthroscopy (LPF and TBW)	OPS	5-782.b7, 5-784.c7, 5-784.d7, 5-784.e7, 5-784.f7, 5-810.04, 5-810.05, 5-810.14, 5-810.15, 5-810.24, 5-810.25, 5-810.44, 5-810.45, 5-810.54, 5-810.55, 5-810.64, 5-810.65, 5-810.74, 5-810.75, 5-810.84, 5-810.85, 5-810.94, 5-810.95, 5-810.x4, 5-810.x5, 5-811.24, 5-811.25, 5-811.34, 5-811.35, 5-811.44, 5-811.45, 5-811.x4, 5-811.x5, 5-812.04, 5-812.05, 5-812.34, 5-812.35, 5-812.94, 5-812.95, 5-812.a4, 5-812.a5, 5-812.e4, 5-812.e5, 5-812.f4, 5-812.f5, 5-812.g4, 5-812.g5, 5-812.h4, 5-812.h5, 5-812.k4, 5-812.k5, 5-812.m4, 5-812.m5, 5-812.x4, 5-812.x5, 5-819.04, 5-819.05, 5-819.14, 5-819.15, 5-819.x4, 5-819.x5
Implant removal (LPF)	OPS	5-787.07, 5-787.17, 5-787.37, 5-787.67, 5-787.77, 5-787.g7, 5-787.k7, 5-810.34, 5-810.35

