Implant removal (TBW)	OPS	5-787.07, 5-787.17, 5-787.27, 5-787.67, 5-787.77, 5-787.g7, 5-810.34, 5-810.35
Revision of the osteosynthesis (LPF and TBW)	OPS	5-785.07, 5-785.17, 5-785.27, 5-785.37, 5-785.47, 5-785.57, 5-785.67, 5-785.77, 5-789.37, 5-78a.07, 5-78a.17, 5-78a.27, 5-78a.57, 5-78a.67, 5-78a.77, 5-78a.87, 5-78a.97, 5-78a.c7, 5-78a.g7, 5-78a.k7, 5-78a.m7, 5-78a.n7, 5-78a.x7, 5-793.07, 5-793.17, 5-793.27, 5-793.37, 5-793.67, 5-793.77, 5-793.87, 5-793.97, 5-793.a7, 5-793.b7, 5-793.c7, 5-793.g7, 5-793.h7,

		5-793.k7, 5-793.m7, 5-793.n7, 5-793.x7, 5-794.07 , 5-794.17, 5-794.27, 5-794.57, 5-794.67, 5-794.77, 5-794.87, 5-794.a7, 5-794.b7, 5-794.c7, 5-794.g7, 5-794.h7, 5-794.k7, 5-794.m7, 5-794.n7, 5-794.x7, 5-824.4 , 5-824.5, 5-825.01 , 5-825.4, 5-825.a, 5-825.m
Resection arthroplasty (for spacer placement)	OPS	5-829.4
Secondary arthroplasty	OPS	5-824.4 , 5-824.5
Arthrolysis	OPS	5-800.64 , 5-800.65, 5-810.24 , 5-810.25, 5-810.94, 5-810.95
Classification of complications and long-term endpoints/events		
Major adverse event		resuscitation, cardiac arrest, myocardial infarction, stroke, acute renal failure, acute liver failure, acute respiratory distress syndrome, sepsis or death from any case
Thromboembolic event		Deep vein thrombosis, pulmonary embolism, ischemic stroke or death from any case
Surgical complications		Adhesive capsulitis, arthrolysis, debridement, frozen elbow, implant removal within first 3 months, infection, infection with antibiotic-resistant germs, joint damage/cartilage damage, luxation, delayed union, non-union/pseudoarthrosis, malunion, nerve injury, vascular injury, osteonecrosis, postoperative stiffness, secondary arthroplasty, secondary arthroscopy, secondary surgery (open) including revision surgery, upper limb amputation
Implant-associated complications (IAC)		Impingement, bursitis, mechanical malfunction or material failure/loosening, periprosthetic or periimplant fracture
Non-implant associated complications (non-IAC)		Infection, infection with antibiotic-resistant germs, hematoma after surgery

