3.2.1. Primary Endpoints

Variable	Definition
Revision	
 - Time from surgery to revision defined above.
Implant removal (only)	
 - Time from surgery to implant removal - Within first 3 months after surgery, an implant removal will also be considered as a surgical complication - No SC is allowed to occur within 3 months and on the same day
Surgical complications (SC)	
 - Time from surgery of OF to surgical complications, with death being considered as a competing risk event.
In-hospital SC rate (IH-SC)	
 - SC after surgery during index hospitalization (yes/no)
In-hospital implant-associated complications (IH-IAC)	
 - IAC after surgery during index hospitalization
In-hospital non-implant associated complications (IH-non-IAC)	
 - Non-IAC after surgery during index hospitalization

Table 3: Primary endpoints

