4.2. Analysis of Primary and Secondary Endpoints

To analyze differences in the treatment groups (TBW versus LPF), a 1:1 propensity score (PS) matching will be performed to guarantee sufficient balance between them. Each patient treated with TBW will be matched with a patients treated with LPF, based on age, sex, fracture complexity, year of treatment, all clinical relevant comorbidities and pharmaceutical therapy at index hospitalization (listed in table 2 “Comorbidities at Baseline” and “Pharmaceutical therapy”). Analysis set will defined by all patients included in the matching.

The balance will be evaluated using risk differences, z-differences and sum of squared z-differences (SSQZ) and will be reported for all variables before and after matching. The hyper-parameter (i.e. caliper with, distance for continuous variables, factors with exact matching) of the PS matching will be chosen in such way that the sum of squared z-differences (SSQZ) will be minimized around the number of variables included in the matching procedure (k), i.e.

$$k/2 \leq SSQZ \approx k.$$

Overlap between matching groups will be presented by the histogram of $logit(p_s)$. The dependency of the Matching partners and thus a stratified evaluation will not be considered.

In-hospital complications and 30-days mortality

All in-hospital endpoints as well as 30-day mortality are given by binary variables. Absolute and relative frequencies for both treatment group will be reported and differences between them will be tested via two-sided χ^2 -independence test. Moreover, a multivariable logistic regression model will be performed to adjust for patient's risk profile. Odds ratio (OR) comparing TBW and LPF for all in-hospital complications and 30-day mortality will be illustrated using forest plots.

30-day mortality will be defined as primary endpoint instead of in-hospital death to avoid bias due to differences in the LOS of both treatment groups. Absolute and relative frequencies for in-hospital death will be reported for the sake of completeness; however, p-values for possible differences will not be interpreted in a confirmatory manner.

Complications during follow-up

The start of observation will be defined by the day of surgery. Median follow-up time will be determined for the entire analysis set using Kaplan Meier estimate (death as censored event).

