For **OS, MAE and TE**, the Kaplan-Meier estimator will be determined for both groups and plotted for the survival functions along with unadjusted 95% confidence intervals (95%CI). Furthermore, at different time points (1 month, 3 months, 1-5 years), the event rates (1- survival function) will be reported with 95%CI and the total number of observed events per group. For the comparison of groups, the Log rank test will be conducted. Multivariable Cox regression models will analyze the impact of baseline variables on the endpoints. The resulting hazard ratios (HRs) will be presented along with its unadjusted 95% confidence intervals and illustrated in forest plots.

For **SC and minor outpatient complications**, death will be considered as a competing risk event. Hence, cumulative incidence function (CIF) determined by Aalen-Johansen estimate and sub-distributional hazards using Fine & Gray Cox models² will be calculated. Groups will be compared with Gray's test. All results were presented in an analog way explain above (plot of CIFs, reporting of CIF at different time points, forest plot for the HRs).

Multiple comparison problem

As mentioned above, patients were grouped by age (i.e. 18-44 years, 45 – 69 years, ≥ 70 years), where younger (<70 years) and older patients (≥ 70 years) will be analyzed (and published) in separate studies. To account for the multiple test problem in each study separately (<70 years and ≥ 70 years), all p-values comparing treatment-effects determined from multivariable analysis of all primary endpoint will be jointly adjusted using Bonferroni-Holm method³ to control the family-wise error rate with respect to the multiple comparison problem. Adjusted p-values will be compared with the overall significance level of 5%.

Time-dependent analysis

Should the evaluation reveal an overlap of the survival curves approximated with Kaplan-Meier, we will further investigate these with a time-dependent survival analysis or landmark analysis with suitably chosen cut-off values. In addition, the time-dependent hazard ratio will be plotted in the form of a step function. All time-dependent analyses will be of an exploratory nature only.

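### The LPF removal list can miss removals coded only 5-787.27 in patients with both TBW and LPF coded, who are allocated to LPF: a label-dependent undercount of unknown size in a primary endpoint

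*Combined protocol and SAP*

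**What the plan says.** Section 2.1 allocates by the first treatment received and gives a rule for patients with both procedures: "If TBW and LPF were coded at the same day and side, patients will be allocated to the LPF groups". Such patients do enter the cohort. Section 2.2 requires only "at least one coded surgical treatment using TBW (OPS 5-793.27, 5-794.17) or LPF (OPS 5-793.k7, 5-794.k7) will be defined as the index case", and Table 1 has no exclusion for having both.

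Table 2 in Section 3.1 has two removal rows:

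- *Implant removal (LPF)*: "5-787.07, 5-787.17, 5-787.37, 5-787.67, 5-787.77, 5-787.g7, 5-787.k7, 5-810.34, 5-810.35"
- *Implant removal (TBW)*: "5-787.07, 5-787.17, 5-787.27, 5-787.67, 5-787.77, 5-787.g7, 5-810.34, 5-810.35"

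The neighbouring rows for open secondary surgery, arthroscopy and revision are labelled for LPF and TBW together. Only removal is split.

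Section 3.2.1 makes *Implant removal (only)* a primary endpoint, defined as "Time from surgery to implant removal". It also links removal to a second primary endpoint, surgical complications (SC): "Within first 3 months after surgery, an implant removal will also be considered as a surgical complication". For the comparison, Section 4.2 states: "To analyze differences in the treatment groups (TBW versus LPF), a 1:1 propensity score (PS) matching will be performed". The multivariable treatment-effect p-values for all primary endpoints are adjusted together by Bonferroni-Holm within each age-defined study.

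**The concern.** Dual-coded patients carry the LPF label although TBW was also coded at the index operation. The one removal code that the plan reserves for TBW is not looked for in them. The same ipsilateral procedure under the same code is thus an event for a patient labelled TBW and a non-event for a patient labelled LPF. That makes outcome ascertainment depend on exposure.

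Nothing later in the plan repairs this. Matching balances baseline variables, not endpoint definitions. The analyses in Section 4.3 only reweight the cohort. They do not list implant removal, and for SC, which they do list, the codes are unchanged. Section 3.3 accepts misclassified side for osteonecrosis on the ground that both groups are affected alike. That reasoning is not available here.

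**Working it through.** **Code lists.** This is a set comparison of the two rows in Table 2.

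- LPF row: 9 codes. TBW row: 8 codes.
- Shared, 7 codes: 5-787.07, 5-787.17, 5-787.67, 5-787.77, 5-787.g7, 5-810.34, 5-810.35.
- LPF only, 2 codes: 5-787.37, 5-787.k7.
- TBW only, 1 code: 5-787.27.
- Union: 7 + 2 + 1 = 10 codes.

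No other row writes out 5-787.27. The last row of the table refers back to the codes above it, but only for outpatient data and for a secondary endpoint.

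**When an event is lost.** A dual-coded patient's removal is missed only if it carries 5-787.27 and none of the nine LPF-list codes. If a shared code, 5-787.37 or 5-787.k7 is recorded at the same operation, the event counts. If such a code follows at a later operation, the event is counted late. An early removal still reaches SC if another SC code is present.

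**Size.** The documents state no removal rate, no number of dual-coded patients and no coding mix, so there is no figure of the plan's to reproduce. Let

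- r = true removal risk, assumed equal in both arms and in dual-coded patients;
- d = dual-coded share of the LPF arm;
- m = share of removals in dual-coded patients that carry 5-787.27 and no LPF-list code.

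Observed LPF risk = r × (1 − d × m), and loss = r × d × m. All inputs below are assumptions.

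| r | d | m | Loss (points) | Observed LPF risk | Ratio to true risk |
|---|---|---|---|---|---|
| 40% | 0% | any | 0 | 40.0% | 1.000 |
| 20% | 2% | 10% | 0.04 | 19.96% | 0.998 |
| 40% | 2% | 25% | 0.2 | 39.8% | 0.995 |
| 40% | 5% | 50% | 1.0 | 39.0% | 0.975 |
| 40% | 10% | 50% | 2.0 | 38.0% | 0.950 |
| 40% | 20% | 100% | 8.0 | 32.0% | 0.800 |

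These figures are for *Implant removal (only)*. They do not carry over to the 3-month SC component, which would need an early-removal risk in place of r.

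**Mirror gap.** The TBW list omits 5-787.37 and 5-787.k7, so a removal coded only that way after conversion from TBW to LPF is lost from the TBW arm. Let c be the converted share of the TBW arm and q the share of their removals coded only with those two codes. Observed TBW risk = r × (1 − c × q). With r = 40% and q = 80%:

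| d | m | c | Observed LPF | Observed TBW |
|---|---|---|---|---|
| 10% | 50% | 2% | 38.0% | 39.36% |
| 5% | 25% | 2% | 39.5% | 39.36% |
| 2% | 25% | 5% | 39.8% | 38.4% |

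With equal true risks, the observed difference can favour LPF, almost vanish, or favour TBW. Conversion from LPF to TBW has the same gap in the LPF arm and would add to the loss there.

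**The case against.** The strongest reply is that this is a narrow gap with an effect that may be negligible. Only removals under one code standing alone are lost. The documents do not describe what the individual 5-787 codes mean, so how often 5-787.27 would stand alone cannot be judged from them. Coding of both procedures on one day and side does not prove that both implants stayed in place. All of this stands, and it limits any claim about size.

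A second reply is that the plan never says outright that each list applies only to its own arm. That is true. But the labels, set against the jointly labelled neighbouring rows, make it the natural reading, and if both lists were meant for dual-coded patients, the plan needs to say so.

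A third reply is that tying removal to the index implant is a legitimate definition. Conversions already count as revisions, and through revision surgery as SC. That is a fair defence for converted patients. It does not help dual-coded patients, for whom TBW was itself part of the index operation.

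A reader might infer that wire removal in dual-coded patients is never counted, or that the primary removal comparison as a whole is biased in favour of LPF. The documents support neither. Removals that also carry an LPF-list code are counted, and the mirror gap after TBW-to-LPF conversion works in the opposite direction. Nor do all conversion losses add to the LPF deficit: those in the TBW arm offset it.

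**Conclusion.** The gap is real and can be verified from the text. Followed as written, the plan ascertains a primary endpoint, and one component of another, differently by group label in dual-coded patients. Through this route alone the sign is known: removals can be lost only from the LPF arm. The size is unknown. Over the assumed ranges r = 20–40%, d = 2–20% and m = 10–100%, the loss runs from 0.04 to 8 percentage points, and it is zero if d or m is zero. The net direction of the TBW versus LPF removal comparison is not established. This does not invalidate the study, but it is an avoidable asymmetry in a primary comparison and should be closed before the analysis is run.

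**What to change.** At minimum, state in Sections 2.1 and 3.1 that the 10-code union of the two removal rows, ipsilateral, applies to patients with TBW and LPF coded on the same day and side. Use it both for *Implant removal (only)* and for the 3-month removal component of SC. Report the number of these patients in each study (under 70 years, and 70 years and older). Add a sensitivity analysis that excludes them, preferably before matching.

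Using the union list for all patients in both arms, as the main definition or as a sensitivity definition, would also close the conversion gap. Its small downside is that removal of an implant placed at a later conversion is then counted, and conversion rates may differ by arm. The plan should say which definition is primary.

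The cost is an edited table row, one sentence on the allocation rule, and one extra run on claims data already held. The union list sets the undercount from this gap to zero, whatever the unknown rates are.

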2.2. Inclusion and Exclusion Criteria

Within an index period from 01/2011 to 09/2023 all patients will be included, who met all inclusion criteria and no exclusion criterion (see table 1).

Inclusion Criteria
Inpatient coded diagnosis of olecranon fracture (ICD S52.01)
Exclusion Criteria
Incomplete basic information
Incomplete insurance status within two years before index
Previous treatment of olecranon fracture
Unclear treatment of olecranon fracture (other as variable and code from table 2)
Age < 18 years
Coded polytrauma
Bone tumors/ bone metastasis
Both sides injured or missing information of surgery side

Table 1: Inclusion and exclusion criteria.

The first hospitalization within the index period with coded diagnosis for OF (S52.01 main and secondary diagnosis) and at least one coded surgical treatment using TBW (OPS 5-793.27, 5-794.17) or LPF (OPS 5-793.k7, 5-794.k7) will be defined as the index case. In addition, all overlapping cases without time delay (admission date new case = discharge cases with surgery) will be defined as one case-series and will be included in the index case.

3. Endpoints and Variables

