3.1. Variables

The following table lists all variables relevant to the analysis along with their ICD, OPS or ATC codes. For each patient, possible comorbidities will be recorded at baseline by including all outpatient and inpatient information coded within two years prior to the index hospitalization and during first hospitalization (exceptions are marked accordingly).

The "minor outpatient complications" defined below (see the last row of the following table) will be based exclusively on outpatient information coded after discharge of the first hospitalization.

All other variables concerning complications during follow-up will be collected exclusively from inpatient information during hospitalization and after discharge.

Variable	Classification	Code
Olecranon fracture	ICD	S52.01
Simple fracture TBW	OPS	5-793.27
Multi-fragmented TBW	OPS	5-794.17
Simple fracture LPF	OPS	5-793.k7
Multi-fragmented LPF	OPS	5-794.k7
Comorbidities at Baseline		
Alcohol abuses	ICD	E24.4, F10, G31.2, G62.1, G72.1, I42.6, K29.2, K70, K85.2, K86.0, T51.0, T51.9
Arthrosis	ICD	M15-M19 (only before index admission)
Atherosclerosis	ICD	I70
Atrial fibrillation and flutter	ICD	I48
Asthma		J45
Bone tumor/metastasis	ICD	C40.0, C79.5, C79.86, C79.9
Cancer	ICD	C
Chronic kidney disease	ICD	N18, N19
Chronic polyarthritis	ICD	M05, M06
Congestive heart failure	ICD	I50
Coronary heart disease	ICD	I25
Dementia	ICD	F00, F01, F02, F05.1, G30, G31.1
Depressive episode	ICD	F32, F33
Diabetes mellitus	ICD	E10-E14
Dorsalgia	ICD	M54
Hypertension	ICD	I10-I15
Infection	ICD	M86.02, M86.12, M86.22, M86.32, M86.42, M86.52, M86.62, M86.82, M86.92, T84.5, T84.6, T84.7 (only before index admission)
Neurotic, stress-related and somatoform disorders	ICD	F41, F43, F45
Nicotine abuses	ICD	F17
Obesity	ICD	E66
Osteoporosis	ICD	M80-M85
Parkinson	ICD	G20
Polytrauma	ICD, OPS, DRG	ICD: T07 , OPS: 5-982 , or coded DRG started with "W" (only during index hospitalization)
Elbow arthrosis	ICD	M25.52 (only before index admission)
Previous stroke	ICD	I60-I69 (only before index admission)
Prior level of care (LoC)		Level of care in the database (from 2017)
Problems related to care-provider dependency	ICD	Z74

Pharmaceutical therapy		
Any anticoagulant	ATC	B01AA, B01AB, B01AC, B01AE, B01AF, B01AX
Vitamin D or calcium	ATC	A11CC
Bisphosphonates	ATC	M05BA, M05BB
Any osteoporosis pharmacotherapy	ATC	Vitamin D/Calcium or Bisphosphonates
Contraceptives for topical use	ATC	G02B (only for matching)

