4.3. Sensitivity analysis

As a sensitivity analysis, Cox regression analysis for OS, MAE, TE and SC as well as logistic regression analysis for 30-day mortality, IH-MAE, IH-TE and IH-SC will be also performed using the entire OF cohort with different weights:

Approach	Definition of weights	
	Control (LPF)	Treatment (TBW)
Entire cohort with original data*	1	1
Inverse Probability of Treatment Weighting (IPTW) ⁴	$\frac{1}{1 - p_s}$	$\frac{1}{p_s}$
Balanced (or overlap) weighting ⁵	p_s	$1 - p_s$

PS weighting ⁶	$\frac{\min(p_s, 1 - p_s)}{1 - p_s}$	$\frac{\min(p_s, 1 - p_s)}{p_s}$
---------------------------	--------------------------------------	----------------------------------

Table 5: Weighting approaches for sensitivity analysis. *As a first analysis, regression analyses will be performed using the entire cohort without weights. ^{4,5,6} refer to the references. p_s propensity score determined using logistic regression.

5. Treatment of Missing Values

Missing values or inconsistent data in sex, day of birth, exit date of database lead to exclusion from study. For all other variables, no missing data will occur in the study, since all variables will be defined by existing ICD/OPS or ATC codes. If no related code will be found, the according variable will be set to zero. Since the considered comorbidities are highly relevant for any reimbursement, it is very unlikely that they are not coded in the database. However, there could be a bias by setting all the variables as known variables.

6. Software

All statistical analyses will be performed using SAS (SAS Enterprise Guide Version 8.3, SAS Institute Inc., Cary, NC, USA) and R version 4.2.1, R foundation, Vienna, Austria.

References

3. Holm, S. (1979). A Simple Sequentially Rejective Multiple Test Procedure. *Scandinavian Journal of Statistics*, 6(2), 65–70.

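### Patients with the olecranon fracture coded only as a secondary diagnosis are included, but diagnosis position is not adjusted for, which may leave residual confounding by another injury or acute illness

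*Combined protocol and SAP*

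**What the plan says.** Section 2.2 takes as the index case the first stay in the index period with a "coded diagnosis for OF (S52.01 main and secondary diagnosis") together with "at least one coded surgical treatment using TBW (OPS 5-793.27, 5-794.17) or LPF (OPS 5-793.k7, 5-794.k7) will be defined as the index case". The fracture need not be the main diagnosis.

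Section 4.2 matches TBW to LPF patients "based on age, sex, fracture complexity, year of treatment, all clinical relevant comorbidities and pharmaceutical therapy at index hospitalization", with the last two groups taken from Table 2. Section 3.1 collects comorbidities "coded within two years prior to the index hospitalization and during first hospitalization", apart from those marked as pre-admission only. On the matched set, section 4.2 continues: "Moreover, a multivariable logistic regression model will be performed to adjust for" the patient's risk profile; the Cox models use baseline variables. The sensitivity analyses in section 4.3 reweight the whole cohort by a "propensity score determined using logistic regression".

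Among the exclusions in section 2.2 is "Coded polytrauma", which Table 2 defines as "ICD: T07 , OPS: 5-982 , or coded DRG started with" the letter W, during the index stay. Bone tumours or metastases, injury on both sides and unclear treatment are also excluded.

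Section 3.3 states that ICD codes carry no time order within a stay and no laterality. Every listed complication code in the index case is therefore counted as an in-hospital complication. Procedure codes count as surgical complications only when they are ipsilateral.

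**The concern.** When the fracture is a secondary diagnosis, another condition holds the main position. That may be a second injury or an acute illness, and either can raise the risk of complications and death, prolong the stay and increase charges. It could also influence which implant is chosen. If it does both, and the matched arms contain different proportions of such patients, part of the difference between TBW and LPF would reflect the reason for admission.

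The planned diagnostics would not show this. Section 4.2 tunes the matching on the sum of squared z-differences over the variables in the match. A good value says nothing about a variable that is not among them.

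A second problem is misclassification. If a patient was admitted with a stroke, myocardial infarction or sepsis and the fracture is coded second, section 3.3 counts the admission diagnosis as an outcome event.

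**Working it through.** The plan gives no figure on this point, so there is nothing to reproduce. The check sets the sections against each other and then illustrates the possible size.

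**1. Is position used anywhere after inclusion?** Section 2.2 refers to it, so it should be identifiable in the inpatient data. It is not in the Table 2 baseline variables, the section 4.2 matching list, or any term stated for the section 4.3 weights. The regression covariates are not listed one by one, but they are described as baseline variables or risk profile, and Table 2 defines no such variable. No analysis restricted to main-diagnosis patients is planned.

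**2. What is already covered?**
- Covered by exclusion: polytrauma by any of three routes, bone tumours or metastases, and injury on both sides.
- Covered by adjustment: Table 2 comorbidities coded in the index stay, such as heart failure, atrial fibrillation, coronary disease, kidney disease, dementia and cancer.
- Not covered: one further injury that triggers none of the polytrauma routes, because the comorbidity list has no code for an accompanying injury.
- Not covered: an acute illness outside the list. Acute myocardial infarction and sepsis appear in Table 2 only as complications, and stroke enters the baseline only if coded before the index admission.

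**3. Which endpoints are exposed?**
- Most: 30-day mortality, MAE, TE, length of stay and charges, which respond to any serious coexisting condition.
- Also: IH-SC, IH-IAC and IH-non-IAC. These have ICD-coded components (for example infection T84.5 to T84.7, resistant germs U80-83, haematoma T81.0, material failure T85.88 and T85.9) that carry neither timing nor side.
- Least: revision, implant removal and SC during follow-up, which rest mostly on ipsilateral procedure codes.

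**4. How large could confounding be?** Assume no true treatment effect. Let secondary position multiply the risk by R in both arms, and let p1 and p0 be the shares of such patients in the two matched arms. The spurious risk ratio is

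[1 + p1(R − 1)] / [1 + p0(R − 1)].

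All values of p1, p0 and R below are assumptions; the documents give none.

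| p1 vs p0 | R = 1.5 | R = 2 | R = 3 | R = 5 |
|---|---|---|---|---|
| 10% vs 10% | 1.00 | 1.00 | 1.00 | 1.00 |
| 10% vs 8% | 1.01 | 1.02 | 1.03 | 1.06 |
| 10% vs 5% | 1.02 | 1.05 | 1.09 | 1.17 |
| 20% vs 15% | 1.02 | 1.04 | 1.08 | 1.13 |
| 20% vs 10% | 1.05 | 1.09 | 1.17 | 1.29 |

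For example, 20% vs 15% with R = 2 gives 1.20/1.15 = 1.04, and 20% vs 10% with R = 5 gives 1.80/1.40 = 1.29. With equal shares the factor is 1.00 for any R. The formula covers confounding only; it does not measure the misclassification of admission diagnoses.

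**The case against.** The strongest reply is that confounding needs a link between position and implant choice that survives matching on age, sex, fracture complexity, year, comorbidities and drugs, and the documents show none. Nor do they give the share of such patients, which could be small. This stands, and it is why the point is worded as a possibility.

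The exclusions and the index-stay comorbidities already account for many alternative reasons for admission. This also stands: polytrauma is not the only safeguard, and the gap is limited to the remainder in step 2.

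Most primary endpoints depend on ipsilateral elbow procedures, and another reason for admission has no obvious strong route to those. This stands for revision, implant removal and SC during follow-up. It does not stand for the in-hospital primary endpoints with ICD components. It does not help 30-day mortality either, which Table 4 lists as secondary but section 4.2 calls primary.

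Finally, position may not be a clean baseline variable. The plan does not say how it is assigned, ICD codes are dated at discharge, and an index case may join several stays in which the fracture holds different positions. If later events influence it, adjustment would partly condition on a post-treatment variable. This is a fair reason to define the indicator carefully and to show results both ways. It is not a reason to ignore the field.

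**Conclusion.** The gap is real: the plan admits secondary-diagnosis patients and does not use position after inclusion. The consequence is possible residual confounding of unknown size. It is absent if position and implant choice are unrelated after matching. It becomes material only when a clear imbalance meets a strong effect on outcome, as in the lower right of the table.

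A reader might infer that the matched comparison is confounded, or that every secondary-diagnosis patient was in hospital chiefly for something else. The documents support neither reading. They report no association with treatment, and they do not define how the main diagnosis is chosen. A reader might also extend the worry equally to all endpoints; the ipsilateral rule in section 3.3 argues against that for revision, implant removal and SC.

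The change is worth making because the plan already refers to the field, the imbalance would otherwise go unseen, and the misclassification of admission diagnoses falls on the same patients.

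**What to change.** - In Table 2, define a binary variable: S52.01 is the main diagnosis of the stay in which the index TBW or LPF surgery took place. Tying it to that stay settles the case of linked stays.
- Add it to the propensity score, the balance table before and after matching, the multivariable models and the score behind the section 4.3 weights. The number of matching variables k in the balance criterion rises by one. Reporting the share by arm gives the reader p1 and p0 directly.
- Add a sensitivity analysis of the primary endpoints, 30-day mortality, MAE and TE restricted to main-diagnosis patients, with the score re-estimated and matching repeated in that set. Adjustment alone cannot stop an admission diagnosis from being counted as an in-hospital event; the restriction reduces this.
- Report the restricted result beside the adjusted one, because a position coded at discharge may partly reflect later events.

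The cost is one derived variable and one further run of planned analyses. The restricted set is smaller, so its intervals will be wider.
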